10.1 Point of Enrollment

If a subject signs an IRB/IEC approved informed consent form (ICF) and meets all inclusion criteria and fails to meet any exclusion criterion, it is considered that this subject is eligible to be enrolled into this study. The point of inserting any BridgePoint CTO device(s) into the body of the subject is the formal enrollment time point of this subject.

10.2 Withdrawal

All subjects enrolled in the clinical study (including those withdrawn from the clinical study or lost to follow-up) shall be accounted for and documented. Subjects may choose to withdraw from the study at any time, with or without reason and without prejudice to further treatment, although withdrawal is not encouraged. Withdrawn subjects will not undergo any additional follow-up, nor will they be replaced. If a subject withdraws from the clinical investigation, the reason(s) shall be reported. If such withdrawal is due to problems related to investigational device safety or performance, the investigator shall ask for the subject's permission to follow his/her status/condition outside of the clinical study. The investigator may discontinue a subject from participation in the trial if the investigator feels that the subject can no longer fully comply with the follow-up requirements of the trial or if any of the trial procedures are deemed potentially harmful to the subject. Data that have already been collected on withdrawn subjects will be retained and used for analysis but no new data will be collected after withdrawal.

10.3 Enrollment Controls

At least 100 subjects shall be enrolled at 5-10 China sites for this study and each site is allowed to enroll up to 25 subjects.

11. Study Methods

11.1 Data Collection

Data collection schedule of FAST-CTO China study is summarized in Table 11.1-1.

Table 11.1-1: Data Collection Schedule

	Pre-procedure ≤14 days	Pre- procedure ≤3days	Procedure	Post- procedure /prior to discharge	follow-up and visit		
					Telephone or hospital visit at 30 days (±7 days) ^a	Telephone or hospital visit at 6 months (±30 days) ^a	Telephone or hospital visit at 12 months (±30 days) ^a
Informed Consent Form ^b , including date of signature		X					
Demographic data, including age and gender	X						
Physical assessment, including weight and height	X						
Medical history, including diabetes situation	X						
Angina assessment	X			X	X	X	X
LVEF ^c	X						
12 lead ECG		X		X			
Laboratory detection							
Serum creatinine and urea nitrogen	X						
complete blood count ^d	X						
Pregnancy test ^e	X						
Total CK/CK-MB		X ^f		X ^g			
Troponin ^h		X		X			
Cardiac medication	X	X ⁱ	X ⁱ	X ⁱ	X ⁱ	X ⁱ	X ⁱ
Anticoagulant			X				
Antiplatelet drug		X	X	X	X	X	X
Recent previous PCI procedure information		X					

Table 11.1-1: Data Collection Schedule

	Pre-procedure ≤14 days	Pre- procedure ≤3days	Procedure	Post- procedure /prior to discharge	follow-up and visit		
					Telephone or hospital visit at 30 days (±7 days) ^a	Telephone or hospital visit at 6 months (±30 days) ^a	Telephone or hospital visit at 12 months (±30 days) ^a
Procedure, target lesion, pre-dilation, post-dilation (if applicable) and study stent information			X				
Angiography			X				
AE assessment ^j			X	X	X	X	X
ADE、SAE、SADE、UADE、USADE and device deficiency assessment ^k			X	X	X	X	X

a: All follow-up dates shall be calculated according to the index procedure. However, other protocol required follow-ups may be performed via telephone interview or an office visit within the applicable follow-up window.

b: If the study Informed Consent Form is modified during the course of the trial, study subjects will be re-consented, if necessary.

c: LVEF may be evaluated by angiography, echocardiogram, or radionuclide ventriculography within 60 days prior to enrollment.

d: Differential is only required for subjects who have abnormal leukocyte values.

e: A pregnancy test must be performed within 7 days prior to the index procedure in females of childbearing potential.

f: Preprocedure cardiac enzymes can be drawn from the sheath at the time of sheath insertion.

g: A minimum of 1 CK Total or CK-MB draw must be obtained within 1 day after the index procedure. If CK Total values are abnormal (>1× ULN), CK MB or troponin must be run.

h: If neither CK Total nor CK-MB is drawn, troponin must be drawn.

i: Collection is only required for subjects with any changes of cardiac medications.

j: All AEs will be monitored and reported to BSC from the time of enrollment through the 12-month follow-up for all subjects enrolled

k: ADEs, SAEs, SADEs, UADEs, USADEs, and device deficiencies will be monitored and reported to BSC from the time of enrollment through the 12-month follow-up for all subjects enrolled.

Abbreviations: AE= Adverse event; ADE= Adverse device effect; CBC= Complete blood count; CK= Creatine Kinase; CKMB= Creatine kinase isoenzyme; ECG= Electrocardiogram; PCI= Percutaneous coronary intervention; SADE= Severe adverse device effect; SAE= Severe adverse event; UADE=Unanticipated adverse device effect; USADE= Unanticipated severe adverse device effect

11.2 Screening of Study Subjects

This study will store a patient screening log, to record the information of subjects failing to meet eligibility criteria (including screening failure reasons) of FAST-CTO China study.

11.3 Informed Consent

Before any study specific tests or procedures are performed, subjects who meet the clinical eligibility criteria will be asked to sign the IRB/IEC-approved study ICF. Subjects must be given ample time to review the ICF and have questions answered before signing.

Study personnel should explain to the subject that even if the subject agrees to participate in the trial and signs the ICF, catheterization may demonstrate that the subject is not a suitable candidate for the trial.

Refer to section 10.1 for definition of point of enrollment.

11.4 Up to 14 Days Prior to the Procedure

The following preprocedural data shall be collected within 14 days prior to the index procedure (unless otherwise stated):

- Confirmed to meet clinical eligibility criteria
- Demographic data, including age and gender
- Physical assessment, including weight and height
- Medical history (general condition, heart, nerve, kidney and peripheral medical history), including but not limited to the following:
 - Diabetes condition
 - Current angina condition
 - LVEF measured within 60 days prior to enrollment
- Laboratory detection
 - Serum creatinine and urea nitrogen
 - Complete blood count (CBC) and blood platelet
 - Women of child-bearing period are required to conduct the pregnancy test within 7 days prior to the procedure (according to local clinical routine practice, serum and/or urine)
- Current usage of cardiac medications

11.5 Concomitant Medication Required in This Study

For all subjects, a dual anti-platelet therapy (DAPT, i.e., aspirin and clopidogrel) is recommended according to current ACC/AHA/SCAI/ESC guide. Recommended DAPT dose regimen and treatment length are as follows:

Aspirin:

- For subjects who have been taking aspirin \geq 72 hours at the time of the index procedure, a loading dose is not required but recommended. The loading dose shall be described at the investigator's decision .
- For subjects who have not been taking aspirin \geq 72 hours at the time of the index procedure, a loading dose is recommended prior to the procedure (the loading dose is recommended 24

hours prior to the procedure but no later than 2 hours after the index procedure). The loading dose shall be described at the investigator's decision.

- All subjects shall take aspirin indefinitely after the index procedure.

P2Y₁₂ inhibitors

- For subjects who have been taking clopidogrel for \geq 72 hours at the time of the index procedure, a loading dose is not required.
- For subjects who have not been taking clopidogrel for \geq 72 hours at the time of the index procedure, a loading dose is required prior to the procedure (the loading dose is recommended to be prior to the procedure but no later than 2 hours after the index procedure). The loading dose of clopidogrel is recommended as 600mg.
- Subjects must be treated with clopidogrel for at least 6 months following the procedure. For subjects not at high risk of bleeding, clopidogrel treatment shall continue for at least 12 months following the procedure.

Index procedure / cath lab medication: a proper anticoagulant therapy shall be given in the procedure according to local standard treatment practice. If heparin is used, an activated clotting time (ACT) $>$ 250 seconds is recommended in the whole procedure.

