Required Therapy	
Based on the American College of Cardiology (ACC)/American Heart Association (AHA)/Society for Cardiovascular Angiography and Interventions (SCAI) guidelines^{ab}, and supported by the European Society of Cardiology (ESC) guidelines^c, dual antiplatelet therapy with aspirin and a clopidogrel is prescribed as follows to reduce the risk of thrombosis.
 
Aspirin:
 
 For subjects who have been taking aspirin for \geq 72 hours at the time of the procedure, a loading dose is not required. But a 75-325 mg aspirin is recommended prior to the index procedure. For subjects who have not been taking aspirin for \geq 72 hours at the time of the procedure, a loading dose is recommended 24 hours prior to the index procedure, where the loading dose shall be decided by the investigator. Subjects shall take aspirin indefinitely after the index procedure. 
Thienopyridine
 
 For subjects who have been taking clopidogrel for \geq72 hours at the time of the index procedure, a loading dose is not required. For subjects who have not been taking clopidogrel for \geq72 hours at the time of the index procedure, a loading dose is required. It is recommended that the loading dose be administered prior to the index procedure. However, in all cases, the loading dose is required to be administered not more than2 hours after the index procedure. 
The following loading doses are recommended:
 
 o Clopidogrel: A peri-procedural loading dose of 600 mg is recommended. 
Subjects must be treated with clopidogrel for at least 6 months following the index procedure. In subjects not at high risk of bleeding, clopidogrel treatment should continue for at least 12 months following the index procedure.

Key Inclusion Criteria	
Clinical Inclusion Criteria:
 
CI1. Subject must be \geq 18 but $<$ 80 years of age
 
CI2. Subject (or legal guardian) understands the trial requirements and the treatment procedures and provides written informed consent before any trial-specific tests or procedures are performed
 
CI3. Subject is eligible for percutaneous coronary intervention (PCI)
 
CI4. Subject has symptomatic coronary artery disease or myocardial infarction (MI) with objective evidence of ischemia or silent

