4.1.3 Technical and Procedure Success

Technical success is defined as the placement of a guidewire in the true vessel lumen outside the CTO distal end. Procedure success is defined as a successful recanalization of vessel (TIMI 3 flow). Technical success is realized in all subjects except for seven subjects, and then, revascularization is obtained successfully by drug eluting and/or placement of bare metal stent (37/44, 84%). Various methods are used in the procedure to achieve the success of the procedure. Table 4-1 summarizes the method to achieve technical success.

Table 4-2: Methods of Technical Success

Result	Number of subjects	Percentage of total subjects (%)
Use CrossBoss CTO catheter to enter the true lumen	24	55%
Use CrossBoss CTO Reentry System to reenter the true lumen	12	27%
Use a standard guidewire to cross and reenter	1	2%
Failed case	7	16%
Total	44	100%

Average procedure time is 99.5 ± 61.5 minutes. Average Fluoroscopy time is 32.1 ± 28.1 minutes, and average amount of radiation is 3.6 ± 2.3 Gray.

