4.2.5.2 Primary efficacy endpoint

In total 44 operations on 42 subjects, 28 subjects achieved the placement of the guidewire in CTO distal true lumen. Among them, one subject obtained the success after two procedures. The total success rate was 67% (28/42), slightly lower than the prespecified rate. Although the study only enrolled 42 subjects of the originally planned 100, the success rate was much higher than the historical benchmark result. Therefore, the study met the primary efficacy endpoint.

The study did not prespecify the rate of secondary procedure endpoint, however, its result was very prospective. Total procedure time and total fluoroscopy time incorporated in the literature were 146 minutes and 53 minutes respectively in average [19-23]. Total procedure time is defined as the time from inserting the first guiding catheter to withdrawing the last guiding catheter. The average procedure time of using BridgePoint Medical CTO System devices was 111±62 minutes (comparing to the literature average value, $p < 0.001$). The total X-ray radiation time of is defined

as the total time of exposure to the X-ray throughout the whole procedure. The Fluoroscopy time during the whole procedure was 41 ± 22 minutes (compared with the average literature value, $p = 0.008$). The 30-day revascularization result matches its primary efficacy endpoint result of 28/42(67%).

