4.3.3.4 Primary Efficacy Endpoint

Primary efficacy endpoint of FAST-CTO study is the technical success. Technical success is defined as the ability of the BridgePoint Medical System to successfully facilitate placement of a guidewire in the CTO distal true lumen. The total success rate is 76.7% (115/150) according to lesions and 76.9% (113/147) according to subjects. This result is better than 54%, the lower limit of success rate set in this study, and higher than 61%, the acceptable upper limit. If the true potential success rate is 54%, it is observed that among 150 CTO lesions, 115 or more lesions were successful and p value <0.0001 (provided that these CTO lesions were independent lesions). Similarly, if the true potential success rate is 54%, it is observed that among 147 subjects, 113 or more subjects were successful and p value <0.0001 (provided that the success rate is a constant). Table 4-7 summarizes the technical success rate according to used devices. Although there was no independent classification to support it, the results in all used modes exceeded the primary efficacy endpoint threshold.

Table 4-8: Technical Success Classified by Used Devices

CTO endpoint	Total (n=150)	Only CrossBoss (n=73)	Reentry cases ^a (n=77)	p-value ^b
Technical success	77% (115/150)	77% (56/73)	77% (59/77)	1.00

^a Only includes cases that used Stingray only and used all systems.

^b Using Fisher's Exact test

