11.7 Enrollment and Index Procedure

Use the standard catheter puncture technique to perform the procedure. The time of inserting the first guiding catheter is the start time of the procedure.

During the procedure, the following operation and assessment shall be completed:

- coronary artery angiography: all patients shall receive angiography assessment in the procedure according to standard clinical routine practice. Angiography data and films of enrolled subjects , as well as working records of technical personnel shall be submitted to Angiographic Core Laboratory for qualitative and quantitative analysis, including the confirmation of the guidewire's entry into the vessel subintimal. Angiography data and films of intervention on

non-target vessel in the index procedure do not need to be submitted to Angiographic Core Laboratory.

- Confirm the lesion meets the inclusion criteria of angiography and fails to meet any exclusion criterion of angiography.
-
- When BridgePoint CTO device facilitates a guidewire to cross the target lesion and the guidewire is confirmed to locate in the true vessel lumen or distal collateral branch vessel lumen of target lesion, all subjects shall receive PCI treatment on the target lesion according to local clinical practice, such as using balloon catheters to make pre-dilation, stent implantation, etc., to target lesion.

In this study, before the failure of BridgePoint CTO System device, other devices against CTO (such as Frontrunner, Crosser or SafeCross, etc.) shall not be used, but the intravascular ultrasound-guided true-lumen seeking and tracking (IVUS-TST) is allowed, i.e., the technique in which the guidewire can cross (or re-cross) the true lumen and move forward along the true lumen to the distal vessel under the guidance of IVUS and taking the occluded segment as the target.

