Follow-up Schedule	Subject follow up will occur via telephone contact or clinic visit at 30 days, 6and 12 months post index procedure, for all enrolled subjects.
Study Duration	About 2 years.
Required Medication Therapy	
Based on the American College of Cardiology (ACC)/American Heart Association (AHA)/Society for Cardiovascular Angiography and Interventions (SCAI) guidelines and supported by the European Society of Cardiology (ESC) guidelines, dual antiplatelet therapy with aspirin and a clopidogrel is prescribed as follows to reduce the risk of thrombosis.
 
Aspirin:
 
 
For subjects who have been taking aspirin for <math>\geq</math> 72 hours at the time of the procedure, a loading dose is not required. But a 75-325 mg aspirin is recommended prior to the index procedure.
 
For subjects who have not been taking aspirin for <math>\geq</math> 72 hours at the time of the procedure, a loading dose is recommended 24 hours prior to the index procedure, where the loading dose shall be decided by the investigator.
 
Subjects shall take aspirin indefinitely after the index procedure.
 
 
Thienopyridine
 
 
For subjects who have been taking clopidogrel for <math>\geq</math> 72 hours at the time of the index procedure, a loading dose is not required.
 
For subjects who have not been taking clopidogrel for <math>\geq</math> 72 hours at the time of the index procedure, a loading dose is required. It is recommended that the loading dose be administered prior to the index procedure. However, in all cases, the loading dose is required to be administered not more than2 hours after the index procedure.
 
 
The following loading doses are recommended:
 
Clopidogrel
 
 
A peri-procedural loading dose of 600 mg is recommended.
 
Subjects must be treated with clopidogrel for at least 6 months following the index procedure. In subjects not at high risk of bleeding, clopidogrel treatment should continue for at least 12 months following the index procedure.
 

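### The 6-month clopidogrel minimum, and any loading dose still due after the procedure, have no exception for subjects who leave without a stent, and Protocol 11.5 is unclear on whether the regimen is required or recommended.

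*Protocol*

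**What the plan says.** **Duration.** Protocol 11.5 (P2Y12 inhibitors): "Subjects must be treated with clopidogrel for at least 6 months following the procedure". SAP section 1, like the protocol synopsis: "Subjects must be treated with clopidogrel for at least 6 months following the index procedure". The sentence that follows in each place extends treatment to at least 12 months for subjects not at high bleeding risk. High bleeding risk therefore relaxes only the longer duration, and the 6-month minimum still binds.

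**Load.** Subjects on clopidogrel for at least 72 hours need no load. For the others a load is required, preferably before the procedure. Within that group the synopsis and SAP section 1 add: "in all cases, the loading dose is required to be administered not more than2 hours after the index procedure".

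**Obligation.** The title of 11.5 and the synopsis and SAP row labels call the therapy required. The lead-in of 11.5 presents dual antiplatelet therapy, including its dose and length, as recommended for all subjects.

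**Who is enrolled and who is treated.** Protocol 10.1: "The point of inserting any BridgePoint CTO device(s) into the body of the subject is the formal enrollment time point of this subject". Protocol 11.7 directs PCI of the target lesion on a condition: "When BridgePoint CTO device facilitates a guidewire to cross the target lesion and the guidewire is confirmed to locate in the true vessel lumen" (or in the lumen of a distal collateral). It gives no instruction for a subject in whom crossing fails.

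**Purpose and risk.** The synopsis gives the purpose of the regimen as reducing thrombosis. Protocol 23.3 states that prolonged dual antiplatelet treatment may increase bleeding.

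**The concern.** Enrollment comes before the crossing result is known, so the enrolled population includes failures by design. The drug rule is written as if every enrolled subject goes on to receive a stent. Read literally, a subject whose lesion was not crossed, and who has no stent anywhere, must take clopidogrel on top of indefinite aspirin for at least 6 months, or at least 12 if not at high bleeding risk. If not already on clopidogrel and not loaded beforehand, that subject must also be loaded within 2 hours of a failed attempt. The documents give no reason for a fixed minimum without a stent.

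Protocol section 14 allows an investigator to deviate only to protect a subject in an emergency. That would cover withholding a load after a perforation. It would not obviously cover stopping clopidogrel in a stable, unstented subject, which would count as a deviation if the rule is binding. Because 11.5 uses both recommended and required language, a site cannot tell whether it is.

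The stake is the safety of subjects and clarity for sites. Bypass surgery after failure is a realistic next step: inclusion criterion CI5 requires subjects to be candidates for it, and Protocol 4.1.4 reports two first-in-man subjects who had it after an unsuccessful procedure.

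**Working it through.** **Step 1. Search for an exception.**

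| Question | Where | Answer |
|---|---|---|
| When is a subject enrolled? | Protocol 10.1 | At device insertion, before the crossing result |
| When is target-lesion PCI directed? | Protocol 11.7 | Only after confirmed crossing |
| Is the 6-month minimum tied to a stent? | Protocol 11.5, synopsis; SAP 1 | No |
| Is the 12-month duration tied to a stent? | Same | No, only to bleeding risk |
| Is the post-procedure load tied to a stent? | Same | No; only subjects on clopidogrel for at least 72 hours are exempt |
| Is deviation allowed? | Protocol 14 | Only in an emergency |

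No section of either document exempts a subject who leaves without a stent.

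**Step 2. Reproduce the stated success rates of the earlier trials.**

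- First-in-man (Protocol 4.1.3): 37/44 = 84.1%, stated as 84%. All 37 were revascularized with stents.
- EU (Protocol 4.2.5.2): 28/42 = 66.7%, stated as 67%. The 30-day revascularization count is the same.
- FAST-CTO (Protocol 4.3.3.4): 113/147 = 76.9%, stated as "76.9% (113/147) according to subjects".

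All three agree.

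**Step 3. Technical failure = (n − successes)/n, with exact (Clopper-Pearson) 95% intervals.**

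| Trial | Failures | Rate | 95% CI |
|---|---|---|---|
| First-in-man | 44 − 37 = 7 | 7/44 = 15.9% | 6.6 to 30.1% |
| EU | 42 − 28 = 14 | 14/42 = 33.3% | 19.6 to 49.5% |
| FAST-CTO | 147 − 113 = 34 | 34/147 = 23.1% | 16.6 to 30.8% |
| All three | 7 + 14 + 34 = 55 | 55/233 = 23.6% | 18.3 to 29.6% |

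**Step 4. Subjects not revascularized, where the documents report it.** Only the first-in-man and EU trials do: (7 + 14)/(44 + 42) = 21/86 = 24.4% (95% CI 15.8 to 34.9%). FAST-CTO, with 147 of the 233 subjects, reports technical failure only.

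**Step 5. Scale for 100 subjects.** At the earlier rates there would be about 16, 23 or 33 technical failures, depending on the trial used. This counts failures of the BridgePoint system. It is not an estimate of unstented subjects.

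**Step 6. Why the unstented share may be lower here.**

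- Protocol 11.7 bars other CTO devices only until BridgePoint has failed, so a failure may still be opened and stented.
- The same section contemplates intervention on non-target vessels at the index procedure.
- AI4 limits lesions to under 40 mm, and AE4 excludes moderate to severe calcification. Mean lesion length was 36.0 mm in the EU trial (range 3 to 150) and 32.3 mm in FAST-CTO.

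The documents give no figure for the combined effect of these points.

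**The case against.** The strongest reply is that 11.5 is advice. Its lead-in expressly presents both the dose regimen and the treatment length as recommended under published guidelines, so an investigator may already depart from it. This is partly right, and a reader of the bullets alone might wrongly take the rule as plainly mandatory. But the section title, the verbs in the bullets, and the labels in the synopsis and SAP section 1 all point the other way. The reply exposes a second defect and does not remove the first.

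Three stronger readings are not supported.

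- *Every enrolled subject must be loaded.* Subjects on clopidogrel for at least 72 hours are exempt, and the synopsis wording quoted above applies only to the remaining group. Where a load is given beforehand, as preferred, a failure exception changes nothing. The number of subjects neither pre-treated nor pre-loaded is not given.
- *About one in four subjects in the earlier trials left without a stent.* The documents do not report this for all three trials. The two that report revascularization total 86 subjects, their rates differ twofold, and the EU count is of revascularization, not of stents.
- *Failures will be withdrawn and so drop out of the 6- and 12-month MACE rates.* This is speculative. Protocol 11.9 expects interruption and discontinuation of antiplatelet drugs to be recorded during follow-up. Protocol 10.2 does not name stopping a drug as a ground for withdrawal, and the analysis sets in SAP 4.1 do not depend on adherence.

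Two clinical points also stand. Exclusions CE8, CE9, CE12 and CE14 remove some patients prone to bleeding. An unstented subject may also have another reason for clopidogrel, such as PCI more than 2 weeks earlier, which CE17 permits. Whether clopidogrel helps after a failed attempt cannot be settled from these documents, since the cited guidelines are not reproduced. That argues for individual judgement in unstented subjects, not for a fixed minimum.

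**Conclusion.** The point holds as an omission and a wording inconsistency. The 6-month minimum, and any clopidogrel load still due after the procedure, have no exception for subjects who leave without a stent, and 11.5 contradicts itself on whether the regimen binds. This rests on the text alone.

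The size is uncertain. BridgePoint technical failure was 15.9% to 33.3% across the earlier trials. The unstented share here is unknown, and rescue devices, non-target stents and easier lesions may make it lower. No excess of bleeding is estimated, and the documents would not support one.

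The technical success and 30-day MACE estimates are unaffected. A reader might infer bias in the later MACE rates, but that would require withdrawals that the protocol does not call for. The change is worth considering because it is cheap and removes an unexplained drug requirement from subjects exposed to its stated risk.

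**What to change.** Amend Protocol 11.5 and repeat the wording in the synopsis and SAP section 1.

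1. **Duration.** Limit the 6-month minimum to subjects who receive a stent at the index procedure, in the target or a non-target vessel. Limit the 12-month sentence in the same way. Reword the lead-in of 11.5 so that it says which elements are required and which are recommended.
2. **Load.** For subjects not on clopidogrel for at least 72 hours, keep the load preferably before the procedure. If it was not given then, require it within 2 hours afterwards only in subjects who received a stent, and allow it to be withheld for perforation, tamponade or urgent CABG. This also settles an editorial conflict in 11.5, which makes the pre-procedure load required and then, in its own parenthesis, only recommended.
3. **No stent.** Add: *In subjects without a stent, antiplatelet treatment after the procedure is at the investigator's decision. Stopping clopidogrel is neither a protocol deviation nor a reason for withdrawal, and follow-up continues to 12 months.* A subject with another reason for clopidogrel can continue it.

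**Cost.** A short amendment with ethics committee approval and notice to sites, and a less uniform antiplatelet regimen among unstented subjects. No visit, data item or table is added, because Protocol 11.9 already collects interruption and discontinuation.
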